### **Non Hematologic:**

Any ≥ Grade 4 non-hematologic toxicity will be considered a DLT.

Any non-Hy's law ≥ Grade 3 liver abnormality is a DLT unless it resolves within 72 hours.

Any ≥ Grade 3 infection lasting more than 7 days in the absence of active AML is considered a DLT.

Any ≥ Grade 3 bleeding with thrombocytopenia in the absence of active AML is considered a DLT.

Any ≥ grade 3 non-hematologic toxicity not resulting directly from active leukemia is a DLT, with the exceptions of:

- Alopecia
- Line associated venous thrombosis
- Grade 3 fatigue, anorexia, constipation
- Grade 3 or 4 electrolyte disturbance that resolves within 24 hours with electrolyte correction and is not clinically significant,
- Grade 3 nausea or vomiting that does not require hospitalization or support with total parenteral nutrition and resolves to < grade 2 within 72 hours

The DLT observation period is defined as cycle 1 day 1 until completion of cycle 1 and will require that in the absence of DLT, patients receive at least 14 of the 21 planned doses of TP-0903 during cycle 1 to be considered evaluable for the tolerability check of the phase 1b. In other words, a patient will be considered unevaluable for the tolerability check and phase 1b component if a patient does not complete the DLT observation period due to reasons other than toxicity (e.g. progression). These patients will still be considered evaluable and included in the denominator when analyzing efficacy endpoints.

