## **4. Definition of Dose Limiting Toxicity (DLT)/Dosing Delays and Treatment Modifications**

### **4.1. Definition of Dose Limiting Toxicity (DLT)**

Drug-related toxicity in this population may be difficult to ascertain, given the aggressive nature of the underlying hematologic disease. Investigators will attempt to assign attribution of toxicities to each drug if possible. Toxicity attributed to any of the agents will be considered dose limiting. DLT will be assigned only to adverse events occurring with cycle 1 of therapy.

Patients who experience dose limiting toxicity may continue on trial provided that the toxicity has resolved to at least Grade 2. The National Cancer Institute Common Terminology Criteria for Adverse Events (CTCAE) version 5.0 (<http://ctep.cancer.gov>) will be used to characterize toxicities. However, any adverse reaction that leads to dose reduction or withdrawal will be considered a DLT.

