#### **Hematologic toxicity:**

Any ≥ Grade 4 neutropenia lasting more than 14 days past the end of the cycle (by day 42) in the absence of active AML should be considered DLT. For patients with > 5% blasts, myelodysplastic changes, or evidence of disease by flow cytometry/cytogenetics, failure to recover normal neutrophil count will not be considered DLT as this could be the result of persistent disease. Any patients who stop treatment prior to completing evaluation for the DLT observation period due to disease progression or refusal for further participation for reasons other than toxicity will be replaced for the purposes of dose- finding and safety evaluations.

Other events may occur which do not meet the definition of a DLT but are concerning to the investigators and sponsor and may be then considered to be DLTs. Any other toxicities occurring during subsequent cycles after cycle 1 will lead to dose modifications as specified below. The National Cancer Institute Common Terminology Criteria for Adverse Events (CTCAE) version 5.0 (<http://ctep.cancer.gov>) will be used to characterize toxicities.

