#### **4.2.1.2 Hematologic DLT:**

After the 42 day period and confirmed hematologic DLT: If peripheral blasts are absent AND bone marrow blasts are less than 5%, then the patient may restart study treatment on cycle 2 at the next lower dose level.

After achieving CR, the dose level may be re-escalated at the initiation of next cycle at the discretion of the investigator.

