### Confirmation of Tolerability

TP-0903 monotherapy has been evaluated in solid tumors and found to be safe at a dose level of 50 mg daily. Although we do not anticipate any safety challenges in patients with AML at this dose level, an early tolerability assessment will be included for the first 6 patients enrolled based on a standard Rolling 6 design. If at most one in 6 patients has a DLT (See Section 4), then TP-0903 monotherapy at 50 mg daily will be considered safe and we will proceed with full accrual of the phase 2 study. If however TP-0903 monotherapy at 50 mg daily does not have acceptable toxicity in the first 6 patients, then an additional 6 patients will be treated at a lower dose level of TP-0903 at 37 mg daily, and the same rule will be used to confirm tolerability. Once a tolerable dose level is confirmed, enrollment can continue to the phase 2 component at that dose level.

### Phase 2

At the confirmed tolerable dose level, TP-0903 monotherapy will be assessed for efficacy in a phase 2 component. Efficacy data from patients treated at the confirmed tolerable dose level during the tolerability check will be utilized in the phase 2 portion of the trial. Efficacy will be assessed using Simon's optimal two-stage phase 2 clinical trial design constraining type I and II errors to 10%.

The primary endpoint is the composite CR rate (CR/CRh), defined according to the 2017 ELN AML Recommendation. All eligible patients who start therapy will be considered evaluable for the primary endpoint and included in the denominator when calculating the composite CR rate. In relapsed/refractory adult patients with AML and FLT3 mutations, the ADMIRAL phase 3 study reported a composite CR rate of 34% with the FLT3 inhibitor gilteritinib, which led to improved overall survival (REF). We will therefore test the null hypothesis that the composite CR rate with TP-0903 is 30% versus the alternative hypothesis that it is 55%. By design, if 13 or more of 31 evaluable patients achieve CR/CRh, then there will be sufficient evidence to warrant further study of TP-0903 in this patient population. An interim analysis will occur after 13 patients have response determined. If 4 or fewer of 13 evaluable patients achieve CR/CRh, then the study will be terminated early. If 5 or more of 13 evaluable patients achieve CR/CRh then enrollment will continue as planned for all 31 evaluable patients. The probability of early termination under the null hypothesis is 0.65.

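### DLT observation closes at day 28, but the one specific hematologic DLT cannot be established until about day 42, and the 1-in-6 gate has no stated wait

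*Combined protocol and SAP*

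**What the plan says.** Section 4.1, under the non-hematologic criteria, sets the window: "The DLT observation period is defined as cycle 1 day 1 until completion of cycle 1". A patient without a DLT is evaluable for the tolerability check after completing that window with at least 14 of the 21 planned doses. No later blood count is required. Section 3 makes a cycle 28 days.

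Section 4.1, under hematologic toxicity, lists one specific criterion: "Any ≥ Grade 4 neutropenia lasting more than 14 days past the end of the cycle (by day 42) in the absence of active AML". Persistent disease (more than 5% blasts, myelodysplastic changes, or disease by flow cytometry or cytogenetics) excludes a patient from it. Section 4.2.1.2 uses the same clock, acting "After the 42 day period and confirmed hematologic DLT". If blasts are absent from the blood and below 5% in the marrow, "then the patient may restart study treatment on cycle 2 at the next lower dose level".

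Section 10 (Confirmation of Tolerability) states that "an early tolerability assessment will be included for the first 6 patients enrolled based on a standard Rolling 6 design", and gives the rule: "If at most one in 6 patients has a DLT (See Section 4), then TP-0903 monotherapy at 50 mg daily will be considered safe". Then: "Once a tolerable dose level is confirmed, enrollment can continue to the phase 2 component at that dose level". No follow-up day is given. The phase 2 toxicity rule is applied continuously but evaluated during the first cycle, from a table that runs from 7 to 31 patients.

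**The concern.** Two clocks in one section disagree. A disease-free patient with ongoing grade 4 neutropenia on day 28 has completed the defined observation period and satisfies the evaluability rule, yet may become a DLT two weeks later. Section 10 takes its DLT definition from Section 4 and so inherits the gap.

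Finding a tolerable dose is the first primary objective, and the gate is the rule that decides it. The timing error runs in one direction: a count of 0 or 1 at the gate can become 2 after phase 2 enrollment has begun, and no rule says whether the gate decision is then reopened.

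The phase 2 table is a weak substitute. If it counts the first six patients, as its 7-31 columns suggest, a count of 2 in 6 fails the gate but does not suspend accrual under the table.

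**Working it through.** **1. Dates.** The cycle is 28 days (Section 3) and the criterion needs more than 14 days beyond it (Section 4.1): 28 + 14 = 42, which reproduces the protocol's own day 42. Strictly, the criterion is met only after that day. Observation therefore closes 14 days before the criterion can be met.

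**2. Who is unresolved when the gate is read.** Suppose the gate is read on the sixth patient's day 28. That patient is unresolved, as is anyone enrolled in the 14 days before the sixth. With random (Poisson) accrual at the 1-2 patients per month in Section 10, the number unresolved is U = 1 + min(5, Poisson(14/30.44 × rate)).

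| Accrual per month | Poisson mean | Mean U | P(U ≥ 3) |
|---|---|---|---|
| 1 | 0.46 | 1.46 | 0.08 |
| 2 | 0.92 | 1.92 | 0.23 |

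**3. How often the gate opens on a count that later fails.** Assumptions, not in the documents: other DLTs have probability 0.15 per patient, and a day-42 event has probability h among otherwise DLT-free patients, all independent. A resolved patient has a DLT with probability 1 − 0.85(1 − h); an unresolved one shows a DLT with probability 0.15 and may add a late one.

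Simplest case, U = 1 and h = 0.05: exactly one DLT among the five resolved patients, then a late event in the sixth.
- One DLT in five: 5 × 0.1925 × 0.8075⁴ = 0.409.
- Late event in the sixth: 0.85 × 0.05 = 0.0425.
- Product: 0.0174.

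Averaging over the distribution of U at 1 and 2 patients per month:

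| h | Total DLT risk | Gate passes, read at day 28 | Gate passes, all events known | Opens, then fails |
|---|---|---|---|---|
| 0.01 | 0.1585 | 0.761-0.763 | 0.756 | 0.005-0.006 |
| 0.02 | 0.167 | 0.746-0.749 | 0.736 | 0.010-0.013 |
| 0.05 | 0.1925 | 0.699-0.707 | 0.674 | 0.025-0.033 |

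**4. The phase 2 table as a backstop.** Its criterion is Pr(p > 0.25 | data) > 0.95 with a Beta(1,1) prior. For 2 DLTs in 6 the posterior is Beta(3,5), giving 0.756, which is below 0.95. The boundaries at 7 and 8 patients are both 4. Starting from 2 in 6, the count at patient 7 is at most 3, so the rule cannot trigger. At patient 8 it triggers only if patients 7 and 8 both have a DLT.

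**5. Effect on the phase 2 table itself.** A late event enters up to 14 days late. At 1-2 patients per month that is 14/30.44 × 1 to 2 = 0.46 to 0.92 patients.

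**The case against.** The best defense is that a sensible team would count the day-42 event. The criterion carries its own window, and Section 4.2.1.2 calls the event a confirmed hematologic DLT. The gate refers to Section 4, and a Rolling 6 design exists to handle patients with pending data. Section 4.1 also lets the investigators and sponsor treat other concerning events as DLTs. Section 5.8 has DLTs discussed at weekly and twice-monthly meetings, with the investigator judging whether to stop.

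Most of this stands. It answers a stronger reading that a reader might infer, namely that hematologic DLTs could never count toward the gate; the documents do not support that. (The clause that "any adverse reaction that leads to dose reduction or withdrawal will be considered a DLT" adds little here, because Section 4.2.1.2 only permits a restart at a lower dose, and only once the DLT is confirmed.) It does not supply the timing. Section 10 names Rolling 6 but writes out only the 1-in-6 rule, and Section 4.1 determines who is still pending; by its window, nobody is after cycle 1. The meetings would discuss a late DLT, but nothing links it back to the gate.

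It is also fair that few patients can meet the criterion. Section 7.1 requires neutrophils of at least 1.0 × 10⁹/L for CR and above 0.5 × 10⁹/L for CRh. Taking grade 4 as below 0.5 × 10⁹/L, patients in CR or CRh at that time are out, leaving mainly some with CRi or a morphologic leukemia-free state. The 5% rate may be generous.

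**Conclusion.** The concern holds as a conflict between stated windows in a safety decision, with a small practical effect. The gate opens on a count that later fails about 0.5-3.3% of the time. This is usually, but not always, because of the last one or two patients enrolled: three or more of the six are unresolved about 8-23% of the time. These figures rest on the assumed 15% and 1-5% rates, independence, random accrual at 1-2 patients per month, and reading the gate on the sixth patient's day 28.

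A reader might infer that the gate would accept an unsafe dose. The calculations do not show that: total DLT risk is 0.16-0.19 in these scenarios, below the 0.25 limit in the phase 2 rule. The Simon two-stage efficacy design is unaffected, since all eligible patients who start therapy enter its denominator. It should still be fixed, because the gate decides a primary objective, the error runs one way, and the remedy is cheap.

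**What to change.** Amend Sections 4.1 and 10 as follows.

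- For a patient without active AML (by Section 4.1's own exclusions, using the marrow already mandated after cycle 1) who has ongoing grade 4 neutropenia at the end of cycle 1, extend the DLT observation period to recovery or day 42. Do not count that patient as DLT-free until then.
- Count an event confirmed at day 42 as a cycle 1 DLT in both the 1-in-6 gate and the phase 2 table.
- Hold the gate only if a pending patient could change the decision, that is, when known DLTs are at most 1 and known plus pending is at least 2.
- Specify a day-42 neutrophil count for pending patients. The Section 9 calendar schedules counts in cycle 2, but for a patient whose cycle 2 is held it leaves them to clinical indication after induction.

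The cost is wording, one blood count in a few patients, and an occasional wait of up to 14 days. With other DLTs at 15% and the accrual model above, treating older pending patients as recovered, a wait is needed about 2.4-3.2%, 4.9-6.5% or 9.9-13.2% of the time if 5%, 10% or 20% of otherwise DLT-free patients are pending at day 28 (again assumed rates).

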#### **Hematologic toxicity:**

Any ≥ Grade 4 neutropenia lasting more than 14 days past the end of the cycle (by day 42) in the absence of active AML should be considered DLT. For patients with > 5% blasts, myelodysplastic changes, or evidence of disease by flow cytometry/cytogenetics, failure to recover normal neutrophil count will not be considered DLT as this could be the result of persistent disease. Any patients who stop treatment prior to completing evaluation for the DLT observation period due to disease progression or refusal for further participation for reasons other than toxicity will be replaced for the purposes of dose- finding and safety evaluations.

Other events may occur which do not meet the definition of a DLT but are concerning to the investigators and sponsor and may be then considered to be DLTs. Any other toxicities occurring during subsequent cycles after cycle 1 will lead to dose modifications as specified below. The National Cancer Institute Common Terminology Criteria for Adverse Events (CTCAE) version 5.0 (<http://ctep.cancer.gov>) will be used to characterize toxicities.

#### **4.2. Dosing Delays/Dose Modifications**

##### **4.2.1 Dosing Delays/Dose Modifications for DLTs:**

###### **4.2.1.1 Non-hematologic DLT:**

**Study treatment will be held for any patients experiencing a DLT.**

Patients experiencing Grade  $\geq$  3 non-hematologic toxicity will have study treatment held until the toxicity resolves to NCI CTCAE  $\leq$  grade 1 or to the patient's baseline values. Patients may restart TP-0903 at the next lower dose level when the adverse event recovers to CTCAE  $\leq$  grade 1. If study treatment is restarted and another non-hematologic DLT (Grade  $\geq$  3) is encountered at the lower dose, the patient must be removed from the study. If the non-hematologic toxicity does not recur on re-challenge, the dose level may be re-escalated at the initiation of next cycle at the discretion of the investigator. Study treatment will be discontinued permanently for any grade 4 non-hematologic DLT.

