#### **TP-0903 MONOTHERAPY FOR AML PATIENTS WITH FLT3 MUTATIONS AND RELAPSED/REFRACTORY DISEASE**

AML patients with FLT3 mutations and relapsed/refractory disease are eligible to receive TP-0903, at a starting dose of 50 mg daily as a single agent for days 1-21 of a 28-day cycle. If the 50 mg dose does not meet the tolerability criteria, a lower dose level of 37 mg daily as a single agent for days 1-21 of a 28-day cycle will be considered.

Dose Level	TP-0903 (D1-21) (mg/day PO)
-1	25
0	37
1	50

Patients may continue treatment indefinitely for as long as clinical benefit is achieved per the investigator's judgment. Bone marrow examinations for disease response assessment will be mandated after the first cycle and at the end of treatment. Subsequent bone marrow examinations may be completed at the discretion of the treating physician.

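### Re-escalation after a DLT is not tied to the tolerability check, so a patient reduced to 37 mg may be returned to 50 mg after 50 mg has failed (minor, patient safety)

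*Combined protocol and SAP*

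**What the plan says.** **Individual dosing after a DLT.** Under Section 4.2.1.1, treatment is held after a DLT, and then "Patients may restart TP-0903 at the next lower dose level when the adverse event recovers". Next comes the re-escalation clause, at the investigator's discretion: "If the non-hematologic toxicity does not recur on re-challenge, the dose level may be re-escalated at the initiation of next cycle". Two limits stand beside it. A further non-hematologic DLT at the lower dose removes the patient from the study, and "Study treatment will be discontinued permanently for any grade 4 non-hematologic DLT". For a hematologic DLT, Section 4.2.1.2 permits a restart in cycle 2 at the next lower level if blasts have cleared, and adds: "After achieving CR, the dose level may be re-escalated at the initiation of next cycle at the discretion of the investigator".

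**Staying on treatment.** Section 4.1 states: "Patients who experience dose limiting toxicity may continue on trial provided that the toxicity has resolved to at least Grade 2". Section 3 sets no end to treatment: "Patients may continue treatment indefinitely for as long as clinical benefit is achieved". It lists the levels as 50, 37 and 25 mg.

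**Cohort decision.** Section 10, Confirmation of Tolerability, accepts 50 mg on this condition: "If at most one in 6 patients has a DLT". If 50 mg does not pass, "then an additional 6 patients will be treated at a lower dose level of TP-0903 at 37 mg daily", and the same rule is applied there. Nothing is said about patients already on study when a level fails.

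**The concern.** The first primary objective is to find a tolerable dose, and the six-patient check is how the trial answers it. The re-escalation conditions look only at the individual: recovery, a restart one level down, then no recurrence (non-hematologic) or CR (hematologic). None of them asks whether the dose being returned to has since failed the check.

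The patients concerned are those who have already had a DLT at that dose. Tolerating 37 mg, or reaching CR after the reduction, is not evidence that they would tolerate 50 mg. What is at stake is the safety of those patients.

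**Working it through.** The plan gives no figure on this point, so the check sets the provisions side by side and then asks how often the branch could be reached.

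**1. Is the path open?** Take a patient in the first cohort with a grade 3 non-hematologic DLT at 50 mg.

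- Section 4.1: the patient may stay on trial.
- Section 4.2.1.1: after recovery to grade 1 or baseline, the patient restarts at 37 mg. If the toxicity does not recur, 50 mg is allowed again from the next cycle.
- Section 10: failure of 50 mg leads to new patients being treated at 37 mg. It puts no restriction on this patient.
- Section 5.8: DLTs are discussed and the trial's risk/benefit is reviewed, but no individual dose is capped.
- Section 10, excessive-toxicity rule: it applies after tolerability is confirmed and suspends accrual. It does not set the dose of a treated patient.

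No provision closes the path. The hematologic route in 4.2.1.2 is open in the same way, with CR as its condition.

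**2. Is the timing unusual?** No. With its second DLT a level can no longer pass. For the patient with the second or any later DLT, any re-escalation must come after that. For the patient with the first DLT it may, because re-escalation has to wait for recovery, a restart and a new cycle.

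**3. How often could a level fail?** Let X be the number of DLTs in 6 evaluable patients, X ~ Binomial(6, p). The level fails if X ≥ 2:

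P(fail) = 1 − (1 − p)^6 − 6p(1 − p)^5

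| Assumed true DLT rate p | (1 − p)^6 | 6p(1 − p)^5 | P(fail) |
|---|---|---|---|
| 10% | 0.531 | 0.354 | 0.114 |
| 20% | 0.262 | 0.393 | 0.345 |
| 25% | 0.178 | 0.356 | 0.466 |
| 30% | 0.118 | 0.303 | 0.580 |

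To two decimals, from unrounded values: 0.11, 0.34, 0.47 and 0.58. The rates are assumptions, since the documents give no DLT rate in AML at 50 mg. The 25% row is the acceptable level used in Section 10's excessive-toxicity rule. Section 10 itself expects no safety challenges at 50 mg.

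**4. What must happen besides failure?** At least one patient must have had a DLT of a type with a re-escalation clause, recovered, restarted at the lower dose, continued to benefit, then had no recurrence or reached CR, and been re-escalated by choice of the investigator. Each step can only lower the probability, so P(fail) is an upper bound. The documents give no figure for any of these steps.

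**The case against.** The strongest reply is that the two sets of rules do different jobs. Section 10 chooses the dose for the next cohort and for phase 2. Section 4.2.1 manages one patient from that patient's own course, under several conditions and with permissive wording. Keeping them apart is a coherent choice. The safeguards are also real: under Section 5.8 DLTs are discussed at weekly and twice-monthly meetings with minutes, and the data and safety monitoring committee receives quarterly reports. Toxicity in later cycles leads to dose modification (4.1), and in maintenance a grade 3 related event means hold and reduce and a grade 4 event means stop (4.2.2.2).

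This keeps the point small but does not remove it. Review meetings inform a decision; they do not bar one. Later dose modification acts only after toxicity has returned. DLTs are assigned only in cycle 1, so toxicity after re-escalation would not count in either DLT rule, although it would still be recorded as an adverse event.

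A reader might go further in three ways that the documents do not support.

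- **A minimum count of affected patients**, such as one fewer than the number of DLTs. Section 4.1 counts any reaction leading to dose reduction as a DLT, and reductions under 4.2.2.1 have no re-escalation clause. Grade 4 non-hematologic DLTs end treatment, and hematologic DLTs without CR give no route back. A level could fail with no patient eligible to be re-escalated.
- **Reading 0.11 to 0.58 as a risk of harm.** These are probabilities that a level fails, nothing more.
- **Requiring everyone at a failed level to step down.** Patients without a DLT may still be taking 50 mg, and Section 10 does not move them. Forcing down a re-escalated patient who now tolerates 50 mg, while the others stay on it, would be inconsistent.

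**Conclusion.** The point holds in a narrow form and is minor. The protocol expressly permits a patient who had a grade 3 non-hematologic DLT, or a hematologic DLT followed by CR, to be returned to a dose that the trial has judged not tolerable. This rests on reading 4.2.1.1, 4.2.1.2 and Section 10 together; no other provision caps the dose.

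On size, the branch is reached only if a level fails, with the probabilities shown above under the assumed rates and a common, independent DLT risk. Those values bound the frequency from above. The number of patients affected cannot be estimated, because nothing in the documents says how often investigators would re-escalate. The two-stage efficacy design, its error rates and the toxicity boundaries are untouched.

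**What to change.** Add one sentence to each of 4.2.1.1 and 4.2.1.2: *A patient who had a DLT may not be re-escalated to a dose level that has failed the tolerability check (2 or more DLTs).*

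The wording covers 37 mg as well as 50 mg. Whether patients who are already tolerating a failed level stay on it is a separate decision, which this sentence leaves open.

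The cost is an amendment of one sentence in two places, with no change to sample size, error rates or the monitoring table. The downside is slightly less investigator discretion, for example for a patient in CR after a hematologic DLT whom the investigator would have wished to return to the higher dose.
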